## Specific Aims

Pain management after major abdominal surgery remains challenging. The best-accepted traditional analgesic approach is continuous epidural analgesia. However, epidural analgesia is rapidly being replaced by transversus abdominis plane (TAP) blocks. TAP infiltration is an alternative to epidural blocks for providing postoperative analgesia to the anterior abdominal wall. TAP infiltrations are relatively easy to perform, generally safe, and can be performed in patients who are anti-coagulated. TAP infiltration can be performed as a single injection, or a catheter can be inserted for continuous local anesthetic infusion.

Single shot plain bupivacaine is often used for TAP blocks, but plain bupivacaine provides <24 hours of analgesia. Catheters provide analgesia for longer, but they are difficult to position properly and difficult to maintain in the proper anatomical location. An alternative to TAP catheters is infiltration of liposomal bupivacaine which, in other sites, lasts up to three days. But whether liposomal bupivacaine is preferable to plain bupivacaine for TAP blocks remains controversial, with available studies being sparse and inconclusive.

We therefore proposed to compare single-shot TAP infiltration with liposomal bupivacaine, plain bupivacaine, and placebo on length of anesthetic effect determined by the opioid consumption. We will evaluate the following specific aims, all of which will be assessed over 72 hours, or the duration of hospitalization if shorter:

**Primary Aim 1:** To assess the relative effects of TAP blocks with liposomal bupivacaine, plain bupivacaine and placebo on cumulative opioid consumption in first 24 hours with TAP blocks.

**Primary Aim 2:** To assess the relative effects of TAP blocks with liposomal bupivacaine, plain bupivacaine and placebo on cumulative opioid consumption in 24 to 48 hours with TAP blocks.

**Secondary Aim 1:** To assess the relative effects of TAP blocks with liposomal bupivacaine, plain bupivacaine and placebo on the duration of abdominal wall analgesia (determined by pinprick and cold).

**Secondary Aim 2:** To assess the relative effects of TAP blocks with liposomal bupivacaine, plain bupivacaine and placebo on pain after surgery in first 72 hours.

**Secondary Aim 3:** To assess the relative effects of TAP blocks with liposomal bupivacaine, plain bupivacaine and placebo on cumulative opioid consumption 48 to 72 hours.

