**Placebo group;** patients will receive total of 80 ml of normal saline, injected 20 ml in each of the four-quadrant sites.

General anesthesia will be induced using propofol or etomidate, fentanyl, and rocuronium to facilitate intubation. Anesthesia will be maintained with sevoflurane or isoflurane, along with opioids and muscle relaxants as clinically indicated. However, intraoperative analgesic use will be limited to fentanyl, a short-acting opioid.

Postoperatively, patients will be given intravenous patient-controlled analgesia and nurses will be free to give additional opioid as clinically indicated. Hydromorphone will be the default drug, but fentanyl will be substituted if necessary. Clinicians blinded to trial drug will adjust analgesic management as necessary in an effort to keep verbal response pain scores (details below) <4 points on a 0-10 scale, with 10 being worst pain. When patients no longer need PCA, they will be switched to as-needed hydromorphone or fentanyl.

A single dose of dexamethasone (4-8 mg) will be given to all patients for PONV prophylaxis, and inhaled steroids will be permitted as necessary to treat reactive airway disease. The use of non-steroidal anti-inflammatory drugs and gabapentinoids will be allowed as part of the ERAS approach (enhanced recovery after surgery) according to hospital's clinical practice. Other opioid-sparing medications such as ketamine and lidocaine patches will not be permitted through the initial 72 postoperative hours. Vital

signs and patient activity will be continuously monitored and recorded with a wireless monitor (ViSi mobile, Sotera Wireless, San Diego, CA). Monitoring will be started about 30 minutes after arrival in the postanesthesia care unit and continued for 72 hours while patients remained hospitalized. Clinicians will be blinded to continuous monitoring data; clinical decisions therefore will be guided by routine intermittent vital signs which were typically obtained at 4-hour intervals.

Patients will be allowed to receive prophylactic anti-emetic (first choice ondansetron) intraoperatively based on the risk assessment for nausea and vomiting. Postoperative anti-emetics for symptomatic treatment will also be allowed; again ondansetron will be the first choice.

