## **F. Data Analysis**

Randomized groups will be compared for baseline balance using standard descriptive statistics and the standardized difference (difference in means or proportions divided by the pooled standard deviation).

**Primary Outcomes.** *Opioid consumption.* The following tests for superiority on opioid consumption will be conducted (see type I error control below): 1) 0-24 hours post-surgery: compare each of exparel and plain bupivacaine to placebo; and 2) 24-48 hours post-surgery: compare exparel to each of plain bupivacaine and placebo. Groups will be compared using linear regression on log-transformed morphine equivalents, with results reported as ratio of geometric means between each pair of interventions.

**Type I error control across Primary outcomes 1 and 2.** We will use a parallel gatekeeping procedure to control the type I error at 5% across the 2 primary outcomes. The 2 comparisons for the 0-24 hour period will constitute Set #1, and the 2 comparisons for the 24-48 hour period will constitute Set #2. Within each set we will use the Holm-Bonferroni (HB) multiple comparison procedure among the two comparisons. If either test in the first Set is significant (HB: significance criterion of 0.025 for smaller P-value and 0.05 for the larger), analysis will continue to Set #2. Otherwise, Set #2 will not be analyzed. If analysis proceeds to Set #2, the overall alpha for Set #2 will be  $0.05 \times$  proportion of significant tests in Set #1 (i.e., Set #2 alpha = either  $0.05 \times 1$  or  $0.05 \times .5 = 0.025$ ).

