## **Secondary Outcomes.**

*Time to return of sensation.* We will compare the 3 randomized groups on the time to detection of return of sensation (see above; i.e., when patients feels both ice and pinprick in at least 6 of the 8 designated test locations, or  $\geq 75\%$  of the covered points if the TAP block did not initially cover all eight locations) using a time-to event Kaplan-Meier analysis and log-rank test, and comparing patients on the estimated median time to return of sensation. If all patients do have return of sensation (as expected), the analysis will be equivalent to a Wilcoxon rank sum test, and so this test and the corresponding Hodges-Lehman estimator of median difference (CI) will be reported as a sensitivity analysis. The significance criterion for each of the 3 comparisons will be  $0.05/3 = 0.0167$  to control the type I error at 0.05 for the primary outcome.

*Pain score.* We will compare the 3 randomized groups on mean pain score over the first 72 hours using a linear mixed effects model in which we adjust for within-subject

correlation assuming an autoregressive correlation structure (or unstructured or other, whichever fits best; but making sure to also account for the differences in timing between the measurements) with fixed effects of treatment and categorical time. While we will assess the treatment-by-time interaction, main results will be reported collapsing over time regardless of a significant interaction.

*Opioid consumption 48-72 hours.* This will be analyzed using linear regression as with the primary outcomes.

[figure not shown]
Type I error will be controlled at 0.05 for secondary outcomes by using a significance criterion of  $0.05/3=0.017$  for each outcome.

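### Time to return of sensation carries two conflicting alpha levels: settle its familywise level, then replace the fixed 0.0167 per pair with Holm or a closed test inside that level

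*Combined protocol and SAP*

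**What the plan says.** Section 3.F, Secondary Outcomes, compares the three arms on time to return of sensation "using a time-to event Kaplan-Meier analysis and log-rank test". For the pairwise tests it states "The significance criterion for each of the 3 comparisons will be" 0.05/3 = 0.0167, "to control the type I error at 0.05 for the primary outcome". No step-down, ordering or recycling is given.

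The same section ends with a second rule: "Type I error will be controlled at 0.05 for secondary outcomes by using a significance criterion of" 0.05/3 = 0.017 for each outcome. There are three secondary outcomes: return of sensation, pain score, and opioid consumption at 48-72 hours. Amendment 1 lists abdominal wall sensation as secondary and opioid consumption as primary. The Economic Analysis paragraph also still calls time to return of sensation primary.

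For the two primary outcomes, Section 3.F uses a step-down method: "Within each set we will use the Holm-Bonferroni (HB) multiple comparison procedure among the two comparisons".

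The placebo is inactive: in Section 3.D "patients will receive total of 80 ml of normal saline". The Specific Aims say that "plain bupivacaine provides <24 hours of analgesia" and that liposomal bupivacaine lasts up to three days at other sites. They describe liposomal versus plain as the open question.

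**The concern.** Two things look wrong together.

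First, the factor 1/3 is used twice for different purposes: once to split 0.05 over three pairs within this outcome, and once to split 0.05 over three secondary outcomes. Both cannot hold. The pairwise rule spends the whole 0.05 on this outcome; the closing rule gives it 0.017.

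Second, fixed Bonferroni reserves two-thirds of whatever this outcome receives for comparing a local anesthetic with saline on numbness, and never returns it. Liposomal versus plain, the question behind Secondary Aim 1, stays at one-third whatever the placebo comparisons show. Holm rejects everything that Bonferroni rejects at the same familywise level, under any dependence.

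At stake is power for liposomal versus plain on block duration. It may also affect the cost-effectiveness analysis, which is run only if a difference between the two anesthetic blocks is found and which uses time to return of sensation in its denominator.

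**Working it through.** **Inputs from the plan.** Three pairwise tests at 0.05/3; 0.05/3 for each secondary outcome; 67 per group before and 79 per group after the interim-analysis adjustment (Section 3.G); all patients expected to regain sensation (Section 3.F), so two arms give 2 × 67 = 134 or 2 × 79 = 158 events.

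**Assumptions.** Two-sided tests, proportional hazards, and the hazard ratios (HR) below. The plan gives no effect size or power for block duration.

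**1. The plan's figure.** 0.05/3 = 0.016667, which rounds to 0.0167 (or 0.017). It reproduces.

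**2. What the written rule spends.** Bound for this outcome: 3 × 0.0167 = 0.05. If the outcome's level is 0.017, a compliant Bonferroni is 0.0167/3 = 0.05/9 = 0.0056 per test.

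**3. Holm steps (smallest, middle, largest P).**
- Level 0.05: 0.0167, 0.025, 0.05.
- Level 0.0167: 0.0056, 0.0083, 0.0167.

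Once both placebo comparisons reject, liposomal versus plain is tested at the last step.

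**4. Are the placebo comparisons near-certain?** Log-rank tests on interval-assessed data were simulated with 67 and 79 per group and 1,000 runs per scenario. Assumed values were a median plain duration of 6-18 h, 10-50% failed blocks, 2-5 h of surgery, and saline patients recovered at the first assessment. Both placebo comparisons rejected at 0.0167 in every run.

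**5. Power for liposomal versus plain.** Schoenfeld: power = Φ(√(d/4) × |ln HR| − z(1−α/2)), where d is the number of events. The z values are 2.773 (α = 0.0056), 2.394 (0.0167) and 1.960 (0.05).

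Example, d = 134 and HR 0.6: √33.5 × 0.511 = 2.957.
- α = 0.0056: Φ(0.184) = 57.3%
- α = 0.0167: Φ(0.563) = 71.3%
- α = 0.05: Φ(0.997) = 84.1%

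| Per group | HR | α = 0.0056 | α = 0.0167 | α = 0.05 |
|---|---|---|---|---|
| 67 | 0.5 | 89.2% | 94.7% | 98.0% |
| 67 | 0.6 | 57.3% | 71.3% | 84.1% |
| 67 | 0.7 | 23.9% | 37.1% | 54.2% |
| 79 | 0.5 | 94.3% | 97.5% | 99.2% |
| 79 | 0.6 | 66.9% | 79.3% | 89.4% |
| 79 | 0.7 | 29.8% | 43.9% | 61.1% |

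If the level is 0.05, compare the last two columns: written rule against Holm. If it is 0.017, compare the first two: compliant Bonferroni against Holm. In that case Holm's column is the threshold already printed.

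One simulated case agrees. With medians of 12 h and 18 h, 10% failed blocks and 67 per group, power was 71.9% at the fixed 0.0167 and 84.3% with Holm at 0.05.

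**6. Error across the three secondary outcomes**, taking the other two as held at 0.0167 each.

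| Rule for this outcome | All nulls true | Both placebo nulls false |
|---|---|---|
| Written: fixed 0.0167 per pair | 0.05 + 0.0167 + 0.0167 = 0.083 | 0.0167 × 3 = 0.05 |
| Holm at 0.05 | 0.083 | 0.05 + 0.0167 + 0.0167 = 0.083 |
| Holm at 0.0167 | 0.05 | 0.05 |

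In the right-hand column the only null for this outcome that can be true is liposomal = plain.

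**The case against.** The strongest reply is that fixed Bonferroni is valid and simple, and gives confidence intervals that match the tests; the plan intends to report an interval for the median difference. Choosing Holm for a secondary outcome is an efficiency preference. That stands, and it limits the weight of the point.

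A reader might infer more: that Holm would give liposomal versus plain the full 0.05 at no cost, whichever level the sponsor chooses. The documents do not support this. At 0.017, Holm's last step is the 0.0167 already printed, so nothing is gained over the written threshold; the gain is only over 0.0056, which the plan nowhere prescribes. At 0.05, error control within the outcome is kept, but with both placebo nulls false the bound across the secondary outcomes rises from 0.05 to 0.083. Holm does not worsen the written plan's worst case, since 0.083 is already the bound when all nulls are true. That excess comes from using 0.05/3 twice.

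The size is also not tied to this trial. If the durations in the Specific Aims translate into a large effect, power is near its ceiling either way: at an assumed HR of 0.5 with 67 per group, 94.7% against 98.0%. A material loss appears only at weaker assumed effects.

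Finally, near-certain rejection against saline is an assumption. The recovery rule in Section 3.E counts points initially covered and does not say how a patient with no covered point is scored.

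**Conclusion.** The point holds in a conditional form. The plan contradicts itself on this outcome's familywise level (0.05 or 0.017), and the wording about a primary outcome appears to be left over from before Amendment 1. Until the level is stated, the benefit of a better procedure cannot be stated either.

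- **Level 0.017:** the written rule overspends it threefold in bound (0.05). Holm lets the plan meet its own limit without weakening liposomal versus plain: at an assumed HR of 0.6 and 67 per group, 71% power rather than the 57% of a compliant Bonferroni.
- **Level 0.05:** Holm raises power for that comparison from 71% to 84% at HR 0.6, and from 95% to 98% at HR 0.5. The claim of 0.05 control across the secondary outcomes must then be restated, because the bound is 0.083.

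These figures assume the hazard ratios, two-sided tests, an event in every patient, and rejection of both placebo comparisons with saline patients counted as recovered at the first assessment. This is worth correcting before analysis. It concerns a secondary outcome and does not touch the primary analyses.

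**What to change.** 1. State the familywise level for time to return of sensation, and remove the reference to a primary outcome.
2. Within that level L, replace the fixed criterion by Holm: smallest P at L/3, next at L/2, largest at L. A valid alternative for three groups is an overall log-rank test at L, followed, if it rejects, by each pairwise log-rank test at L. This is a closed test: if one pairwise null is false, at most one other can be true.
3. If L = 0.017, the closing rule on the secondary outcomes can stay. If L = 0.05, rewrite it to say that error is controlled within this outcome and that the bound across the secondary outcomes is 0.083.
4. State how a patient with no initially covered point is scored.
5. Say which confidence intervals will be reported, since intervals matched to Holm or to a closed test are less simple than Bonferroni ones.

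Cost: a sentence or two on the testing rule, short clarifications for items 4 and 5, and no extra patients.

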### **D. Protocol**

After eligibility is confirmed, patients will receive complete information about the study both verbally and in writing. Informed consent will be obtained from the patients prior to randomization and study-specific procedures.

Randomization will be based on computer-generated codes and use random-sized blocks. Allocations will be concealed until the morning of surgery where they will be provided by a web-based system. Randomization will be stratified by study site and chronic opioid use, defined by opioid use for more than 30 consecutive days within three preoperative months, at a daily dose of 15 mg or more of morphine or equivalent. Randomization will also be stratified according to anticipated type of surgery (open vs. laparoscopic-assisted). Clinicians doing the blocks will not be involved in data collection and all the evaluators will be blinded to group allocations.

All blocks will be performed preoperatively or after induction of anesthesia by attending anesthesiologists or regional anesthesia fellows who are experienced in TAP blocks. Premedication will be administered at the discretion of the attending anesthesiologist and standard monitors will be used. Patients will be given 1 g oral acetaminophen an hour before surgery, and an additional 500 mg every 6 hours for 72 hours after surgery starting with oral intake.

Patients will be randomly assigned to: 1) 4-quadrant TAP block with liposomal bupivacaine; 2) 4-quadrant TAP block with plain bupivacaine; or, 3) placebo (normal saline). An in-plane ultrasound will be guide TAP blocks. Two subcostal injections will be applied by placing the probe midline and then moving lateral along the subcostal margin identifying area between the rectus abdominis sheath and the transversus abdominis muscle. The lateral two TAP block injections will be applied in the midaxillary line between

the thoracic cage and iliac crest between external oblique and transversus abdominis muscles. Once the target area is positioned, the following injections will be given, based on randomization:

**Liposomal bupivacaine.** 40 ml of plain bupivacaine 0.25% will be mixed with 20 ml liposomal bupivacaine and 20 ml of saline. 20 ml of the mix will be injected at each location of the 4-quadrant TAP block.

**Plain bupivacaine group.** 50 ml of plain bupivacaine 0.5% will be combined with 30 ml of normal saline making a total of 80 ml. 20 ml will be injected at each location of the 4-quadrant TAP block.

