### **E. Measurements**

Demographic data to be obtained includes height (cm), weight (kg), age (yr), sex, (ASA) physical status, self-declared ethnicity, and the specific type of procedure will be recorded. Patients will be questioned about tobacco and alcohol use, and about illegal drug use. They will also be asked about their medical history including pulmonary disease, kidney disease, diabetes mellitus, neurological disease, chronic pain conditions, previous surgery or stent placement, and medications. Available preoperative laboratory tests and medication list will be recorded. Preoperative pain scores and opioid use will be recorded. Patients excluded for any reason including technical considerations or contraindications will be recorded.

All the procedures for the ultrasound guided TAP blocks will be recorded to the ultrasound and two blinded independent adjudicators will evaluate the success of the blocks. Blocks will be accepted as successful if 3 out of 4 locations were done correctly according to adjudicators.

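### Preoperative pain and opioid use are recorded, but the pain model omits its baseline and the opioid regressions name no covariate, so some precision is given up

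*Combined protocol and SAP*

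**What the plan says.** Section 3.E Measurements commits the trial to collecting both baseline variables: "Preoperative pain scores and opioid use will be recorded".

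Section 3.F Data Analysis then sets out the models:

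- **Pain over 72 hours (secondary).** A linear mixed model with a within-patient correlation structure, "with fixed effects of treatment and categorical time". The preoperative score is not among the terms.
- **Opioid consumption at 0-24 and 24-48 hours (primary).** "Groups will be compared using linear regression on log-transformed morphine equivalents". No covariate is named.
- **Opioid consumption at 48-72 hours (secondary).** "This will be analyzed using linear regression as with the primary outcomes". Again, no covariate is named.

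The one analytic role given to baseline data is descriptive: "Randomized groups will be compared for baseline balance using standard descriptive statistics", together with standardized differences. No rule says what follows if an imbalance is seen.

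Preoperative opioid use does enter the design. Section 3.D Protocol says "Randomization will be stratified by study site and chronic opioid use", where chronic use means more than 30 consecutive days in the three months before surgery, "at a daily dose of 15 mg or more of morphine or equivalent". It adds: "Randomization will also be stratified according to anticipated type of surgery". Preoperative pain is not a stratification factor.

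**The concern.** A patient's pain before surgery, and how much opioid the patient was already taking, can reasonably be expected to predict postoperative pain and opioid consumption. Both are fixed before treatment. In a linear model, prespecified adjustment for such a variable targets the same treatment effect and takes explained between-patient variation out of the residual. The price is about one degree of freedom.

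The pain model is the clearer case. Its fixed effects are listed, and the baseline value of its own outcome is not among them. For the opioid regressions the point rests on silence: no covariate is named there or anywhere else in the document.

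At stake is the width of the confidence intervals. A second, smaller matter is that a balance check with no adjustment rule leaves room to decide on adjustment after the data are seen. Naming the covariates in advance closes that gap.

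**Working it through.** **Inputs.** From section 3.G: ratio of geometric means 0.60, CV 0.85, power 90%, overall alpha 0.05, 67 per group before and 79 per group after allowance for interim looks. From section 3.F: four looks, gamma -4 for alpha and 0 for beta. Assumed, because the documents do not give them: two-sided tests, the per-test alpha behind the 67, and the correlation ρ between baseline and outcome.

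**Step 1: is a covariate gain already built into the sample size?**

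- Effect on the log scale: Δ = |ln 0.60| = 0.511.
- Log-scale SD: σ = √ln(1 + 0.85²) = √ln 1.7225 = 0.737.
- n per group = 2(z₁₋α/₂ + z₀.₉₀)²σ²/Δ².

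This gives 44 at α = 0.05, 52 at 0.025, 60 at 0.0125 and 65 at 0.05/6 (45, 54, 62 and 66 with the t distribution). The stated 67 is within two patients of the result at 0.05/6, which could be read as three pairs in two periods. That alpha is inferred. A numerical group-sequential calculation at that alpha, with non-binding futility, gives an inflation of 1.172, and 67 × 1.172 = 78.5, that is 79. So the plan's figures are consistent with an unadjusted comparison, and no covariate gain appears to be built in.

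**Step 2: what adjustment would be worth.** Residual variance is multiplied by 1 - ρ² and the standard error by √(1 - ρ²). The power columns are for one pairwise test with 67 per group in a fixed design: Φ(Δ/[σ√(1 - ρ²)√(2/67)] - z₁₋α/₂).

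| ρ (assumed) | Variance reduction | SE reduction | 67 becomes | 79 becomes | Power, α = 0.05/6 | Power, α = 0.0125 | Power, α = 0.025 |
|---|---|---|---|---|---|---|---|
| 0 | 0% | 0% | 67 | 79 | 0.915 | 0.935 | 0.961 |
| 0.1 | 1% | 0.5% | 67 | 79 | 0.918 | 0.937 | 0.963 |
| 0.2 | 4% | 2.0% | 65 | 76 | 0.927 | 0.945 | 0.968 |
| 0.3 | 9% | 4.6% | 61 | 72 | 0.941 | 0.956 | 0.975 |
| 0.4 | 16% | 8.3% | 57 | 67 | 0.959 | 0.970 | 0.984 |
| 0.5 | 25% | 13.4% | 51 | 60 | 0.977 | 0.983 | 0.992 |

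The sample sizes show what the gain is equivalent to; they are not a proposal to enrol fewer patients.

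**Step 3: opioid outcomes, beyond the stratum.** The table uses the full correlation of baseline opioid use with the outcome. Part of that may already be carried by the yes/no chronic-use factor. If the indicator alone explains a share s of the variance and indicator plus dose explain R², the further reduction from dose is (R² - s)/(1 - s). As an illustration within the assumed range, take s = 0.2² = 0.04 and R² = 0.3² = 0.09: (0.09 - 0.04)/0.96 = 5.2%, not 9%.

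**Step 4: pain.** The factor 1 - ρ² applies to the between-patient variance of the 72-hour mean score. The documents give no SD for pain, so the gain cannot be expressed in patients.

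**The case against.** The strongest reply is that nothing here is broken. An unadjusted comparison of randomised groups is unbiased with valid type I error, and the primary outcome has power to spare. At 0.025, the first Holm step for the 0-24 hour comparisons, 67 per group gives about 96% power for a single pairwise test. This stands, and it limits the value of the change for the primary outcomes. It does not remove it. If only one 0-24 hour test succeeds, the 24-48 hour set is tested at 0.025 overall, so its first Holm step is 0.0125 and power is 0.935. No comparable power figure exists for pain. Narrower intervals are also useful in themselves.

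It can also be said that the benefit is wholly assumed. The documents give no correlation, no distribution of preoperative pain and no share of patients taking opioids. If most patients have values near zero, the gain could be negligible. This stands too, and is why the result is a range starting near zero.

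Three stronger readings are tempting and are not supported:

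- **That a chance imbalance passes straight into the result.** With 79 per group, the baseline difference between two arms has a standard error of √(2/79) = 0.16 SD. A reader might infer that the outcome comparison is off by that much. The imbalance reaches the outcome only after multiplication by ρ: 0.3 × 0.16 = 0.05 SD to 0.5 × 0.16 = 0.08 SD. Nor is this an additional error. The unadjusted standard error already contains it, so it is the ρ² loss of Step 2 seen from another side.
- **That a preoperative opioid dose is certainly on file.** Section 3.E says opioid use. Applying the 15 mg/day cut needs some dose information, but a continuous daily dose is nowhere stated to be captured.
- **That baseline opioid use plays no part in the trial.** It is a stratification factor, which limits imbalance in chronic users by design. It is the specified analysis models that leave it out.

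**Conclusion.** The point holds as one of lost precision, not of bias or an invalid test. Both baseline variables are recorded, the pain model omits its own baseline, and no covariate is named for any of the three opioid regressions.

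For an assumed baseline-outcome correlation of 0.1 to 0.5, adjustment would lower residual between-patient variance by about 1% to 25%. Below a correlation of about 0.2 the gain is negligible. For the opioid outcomes these are upper figures, because what a finer measure adds beyond the yes/no stratum is smaller. The case is firmest for pain, where the omission is explicit and stratification does not touch the baseline score.

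The conclusion rests on the assumed correlations. The power figures also assume two-sided tests and a fixed design with 67 per group; the 0.05/6 column uses an inferred per-test alpha.

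**What to change.** - **Pain model.** Prespecify the preoperative verbal pain score as a covariate. State that it is not one of the time levels averaged into the treatment effect. This needs saying because section 3.E ties pain scoring to the sensation-testing schedule, whose first measurement comes before the block, and the main result collapses over time.
- **Opioid regressions (0-24, 24-48 and 48-72 hours).** Prespecify preoperative opioid use as a covariate: log(1 + mg/day morphine equivalents) if the daily dose is captured, otherwise the recorded chronic-use indicator. Confirm from the case report form which of these is available.
- **Sample size.** Keep it as planned, since the gain is uncertain.

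The cost is a few lines of SAP text, settled before unblinding, and about one degree of freedom per model. No new data are needed, provided that the fallback indicator is used where dose was not recorded.
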